9.2 Statistical Analysis

Descriptive statistics will be calculated for all variables. A student's t-test will be used to compare the difference in mean changes between the baseline and the end of each arm period while accounting for period and group effects. Data of proteomics will be analyzed by paired student's t-test to identify proteins with statistically significant ($p < 0.05$) changes in normalized spectral counts, and an at least 1.3~1.5-fold will be considered as a physiologically meaningful change to continue the study. The study will be stopped if the changes are not statistically significant or the changes is smaller than 1.3-fold.

10. Human Subject Protection

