place. The participant compliance will be monitored by pill counts at the second and fourth visits. In addition, fatty acid composition of red blood cells will be assessed by GC analysis²⁹. Subjects may be contacted by phone or NIH medical secure email system at least once during each period to monitor compliance and any adverse events. Subjects will also be consented to be contacted for possible future studies. After completion of both arms of the study, results from each participant will be unblinded for possible data analysis.

Table 4. Total amount of fatty acid contained in 12 capsules (12g) consumed per day during trial

| g/12g/day | Control oil (12g) [sardine oil + olive oil] | LCMUFA-rich Saury oil (12g) |
|--------------------|--|--------------------------------|
| EPA+DHA | 2.1 | 1.8 |
| LCMUFA | 0.8 | 3.0 |
| Oleic acid (C18:1) | 4.7 | 0.6 |
| Total saturated FA | 1.5 | 2.4 |
| Total omega-6 | 0.98 | 0.43 |
| Total omega-3 | 2.7 | 2.8 |
| Total MUFA | 5.3 | 4.1 |

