9.1 Sample Size Determination

Sample Size Determination and Methods

The study is designed to be a pilot trial to determine the effect size of the LCMUFA-rich fish oil supplement for a possible future larger clinical trial. The sample size requested in this study is based on our experience on other studies, such as the Omega-3 Fish Oil study. We are requesting to enroll up to 100 subjects to obtain 20* evaluable subjects that complete the whole study, and will perform an interim analysis after 10 subjects have completed both arms in the study. The proteomic analysis makes this study practical and innovative. Based on the information gathered from other studies and on the NHLBI proteomics core experience, the analysis of ten subjects is a realistic number to meet our scientific goals. The interim analysis

will be performed only for proteomic changes, and the magnitude of proteomic change will result in the decision of study continuation. This will allow us to gather sufficient data to estimate changes that could justify a larger study.

* evaluable subjects are subjects that have completed the full time-line of the study (Figure 2), have collected stool specimens and thru the analysis of red cell membrane omega-3 fatty acids (RCM) are found to have taken and absorbed the supplement.*

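### The proteomic test that decides continuation has no period term and names neither its pair nor its fold-change comparator; it should be the period-adjusted LCMUFA-minus-control contrast

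*Combined protocol and SAP*

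**What the plan says.** Section 9 defines the primary outcome, total cholesterol, as an explicit crossover contrast of changes from baseline. Proteomics is a secondary outcome, described only as changes.

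Section 9.2 then gives two tests in consecutive sentences. The general one is a t-test to "compare the difference in mean changes between the baseline and the end of each arm period while accounting for period and group effects". The proteomic one reads: "Data of proteomics will be analyzed by paired student's t-test to identify proteins with statistically significant", with the criterion "statistically significant ($p < 0.05$) changes in normalized spectral counts". The size criterion is that "an at least 1.3~1.5-fold will be considered as a physiologically meaningful change to continue the study", and the negative rule is that "The study will be stopped if the changes are not statistically significant or the changes is smaller than 1.3-fold".

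Section 9.1 restricts the interim analysis, after 10 subjects have completed both arms, to proteomics, and says that "the magnitude of proteomic change will result in the decision of study continuation".

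On the oils, section 2 says the control is matched to the LCMUFA oil on omega-3, and Table 4 in section 3.1 gives the daily grams (control, then LCMUFA) as "Total omega-3 | 2.7 | 2.8". No allocation ratio or blocking is stated.

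**The concern.** The least specified test in the plan carries its only go/no-go decision. Two readings of the pair are open, and each has its own weakness.

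- **Reading A: baseline against end of the LCMUFA period.** The word changes allows this. The test then measures everything that happens while taking the oil, including the effect of omega-3, which the control also supplies. The study could continue for a reason unrelated to LCMUFA.
- **Reading B: LCMUFA against control within subject.** Omega-3 then largely cancels, but any difference between periods enters the paired difference with opposite sign in the two sequences. That inflates the variance and, if the sequences are unequal in size, biases the estimate. The likelier error is to miss a real effect and stop.

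The two harms belong to different readings and cannot both apply to one test.

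**Working it through.** **Inputs from the documents.** Interim n = 10 completers; p < 0.05; at least 1.3-fold. Omega-3 per capsule (Table 3) is 222 mg control and 237 mg LCMUFA. Times 12 capsules this is 2.66 and 2.84 g/day, which reproduces Table 4. EPA+DHA alone is 178 × 12 = 2.14 g against 151 × 12 = 1.81 g, so the match is close but not exact. The plan gives no SD, power or formula for proteomics, so there is no figure of its own to reproduce.

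**Assumed.** SD of the log fold change within a period: 0.2, 0.3, 0.5. Shared omega-3 effect: 1.4-fold. Period shift: 0.5 or 1 SD of the paired difference. Two-sided tests; simple 1:1 randomisation for the split probabilities. Rates marked (s) are simulated, per protein.

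**Reading A, no LCMUFA effect.** The mean log change is ln 1.4 = 0.336, the threshold is ln 1.3 = 0.262, and SE = SD/√10 = 0.063, 0.095, 0.158.

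- Chance that the observed fold reaches 1.3: Φ(0.074/SE) = Φ(1.17), Φ(0.78), Φ(0.47) = 0.88, 0.78, 0.68.
- Requiring p < 0.05 as well (s): **0.88, 0.77, 0.46**. At SD 0.5 the p-value condition is the tighter one.
- Period-adjusted between-oil contrast, same inputs (s): about 0.003, 0.03, 0.05.

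**Reading B.** Write each subject's difference as d = τ ± π + e, where τ is the oil effect, π the period shift (sign set by sequence) and SD(e) = 1.

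- Unadjusted: the mean of d has bias π(n1 − n2)/n. Its expected sample variance is 1 + π² × 4·n1·n2/[n(n − 1)]. At 5/5 with π = 1 that is 1 + 100/90 = 2.11, with no bias.
- Adjusted: the average of the two sequence means, SE = ½·s·√(1/n1 + 1/n2), 8 df. With s = 1 the SE is 0.316 at 5/5, 0.345 at 7/3 and 0.395 at 8/2.

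Power for τ = 1 SD (s):

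| Split | Period shift | Paired, no period term | Period-adjusted |
|---|---|---|---|
| 5/5 | 0 | 80% | 79% |
| 5/5 | 0.5 SD | 72% | 79% |
| 5/5 | 1 SD | **48%** | **79%** |
| 7/3 | 0 | 80% | 72% |
| 8/2 | 0 | 80% | 60% |

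False positives of the unadjusted test, p < 0.05 alone, 1-SD shift (s): 0.7% at 5/5, 1.6% at 6/4, about 6% at 7/3, 20% at 8/2. The bias at 8/2 is 1 × (8 − 2)/10 = 0.6 SD. With a 0.5-SD shift at 8/2 the rate is about 10.5% and the bias 0.3 SD.

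Probability of imbalance: 8/2 or worse is 2 × (45 + 10 + 1)/1024 = 0.11; 7/3 or worse is 2 × (120 + 45 + 10 + 1)/1024 = 0.34.

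**The case against.** **The preceding sentence may already cover proteomics.** It allows for period and group, and section 9 says subjects act as their own controls, so a between-oil pair is a natural reading. But the next sentence names a different test for proteomics and omits those words. Reading A is permitted, not stated.

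**The 20% false-positive rate is a tail case.** This stands. It needs a split of 8/2 and a 1-SD shift. Averaged over splits from simple randomisation, the unadjusted type I error is 5.2% (1-SD shift) or 5.0% (0.5-SD). The 20% also ignores the fold-change condition. With both conditions at 8/2 and a 1-SD shift, the rate is about 1%, 13 to 14% and 20% when the SD of the paired log difference is 0.2, 0.3 and 0.5.

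**Each period has its own baseline.** This stands too. Visit 3 supplies a second baseline. If changes from each period's baseline are paired, a level or assay-batch shift common to a whole period cancels. Only a difference between periods in the change itself remains. The documents give no size for that.

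**Adjustment is not free.** With unequal sequences and no period effect it loses 8 points of power at 7/3 and 20 at 8/2 (80% to 72% and 60%).

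**It is too late.** Section 10.6 says accrual is closed and only data analysis continues. The decision itself cannot be redone, but the remaining analysis can be specified and an interim result re-read.

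**Conclusion.** The point holds as a choice of test that should be changed. The plan gives its deciding analysis a test without a period term and without a named contrast, next to a sentence that supplies the period adjustment for the general analysis.

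The size depends on the reading. Under reading A, a shared omega-3 effect alone can satisfy the rule for a protein about half to nine times in ten. Under reading B, the main harm is lost power when the change differs between periods; bias and excess false positives arise only with unequal sequences. All of this rests on the assumed SDs, shared effect and shifts.

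A reader might infer more: that continuation was in fact driven by omega-3 or drift, that false positives are generally inflated, or that 48% power means a 52% chance of wrongly stopping the study. The documents support none of these. They do not say which pair was used, how the first 10 completers divided by sequence, or how many proteins must meet the rule, so per-protein rates do not translate into a probability for the study decision.

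**What to change.** Replace the proteomic sentence in section 9.2 with a specification along these lines: for each protein, take the log normalised spectral count; compute the change from that period's own baseline (visit 1 to 2, visit 3 to 4); analyse the within-subject difference, LCMUFA minus control, with a period term as for the primary outcome; and apply the 1.3-fold threshold to the back-transformed between-oil estimate. Report how the analysed subjects divide by sequence. If an interim decision was taken on another contrast, say which one and show this contrast beside it.

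The cost is a few lines of wording and a different model call on data already planned, with no new visits or samples. With no period effect, power for a 1-SD effect at n = 10 is 79% instead of 80% when sequences are balanced, 72% at 7/3 and 60% at 8/2. Taking change scores uses no further degrees of freedom; fitting the baselines as covariates would.

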Drug Interactions: Clinical studies have not been done to thoroughly examine the effect of sardine oil- or LCMUFA-rich fish oil supplement with anticoagulants. Patients receiving these fish oil supplements and an anticoagulant or other drug affecting coagulation should be monitored periodically (e.g., aspirin, NSAIDS, warfarin, coumarin).

Stability: LCMUFA or oleic acid-rich fish oil supplement will be maintained and distributed as directed by the supplement manufacturer to maximize maintenance and the quality of active and inactive ingredients in the supplement. Capsules will be initially assigned a 3 year expiration from time of manufacture. Ongoing stability studies will determine if this may be extended. Capsules are not to be frozen.

6. Laboratory Methods

Up to 40 mL of fasting blood will be collected at each visit to perform clinical or research tests. Clinical tests that may be used are listed below and will be performed at the NIH Clinical Center Department of Laboratory Medicine on the second floor of building 10 in the Clinical Center.

Clinical laboratory tests:

- Pregnancy testing
- Liver function test (ALT, AST, bilirubin)
- Uric acid
- Creatinine
- Creatinine kinase (CK)
- Insulin
- Fasting glucose
- Fibrinogen
- PT, PTT
- Whole blood aggregation

17-H-0050: Effect of Fish Oil Enriched In Omega-11 Fatty Acid On Lipoprotein Metabolism In Adults
PI: [name].
Date: May 2, 2019
Version: 5.0 (Amendment D)

- CBC
- hs-CRP
- HbA1C
- TSH
- CBC
- EKG

Clinical lipid and lipoprotein related tests:

- Lipid Panel (Total cholesterol, LDL-C, HDL-C, Triglyceride)
- Lipoprotein Profile (NMR)
- ApoA-I
- ApoB

In addition, we may also conduct some or all of the following research tests: PHA stimulation whole blood, LC-MS-based proteomics, GC-MS-based lipidomics, specific proteins/enzymes related to lipoprotein metabolism (CETP, PLTP, PON, LCAT, LPL), ApoC-II, apoC-III, apoA-V, PCSK9, cholesterol efflux studies, ex-vivo lipolysis study, fatty acid analysis of red blood cells, leptin, adiponectin, blood cell RNA expression, flow cytometry phenotyping of white blood cells, plasma cytokines.

Standard of care laboratory tests and procedures not listed above may be requested and will not be used for research purposes but will only be used to evaluate the patients' health.

7. Data and Biospecimen Management Plan

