The primary outcome measures of this study will be differences between randomized groups in differences between treatment periods in changes from baseline to end of period in the plasma total cholesterol. Secondary outcome measurements will be changes in proteomics, lipoprotein particle number, HDL functional test (i.e. efflux study) composition and size. Each subject will serve as their own control.

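### Section 9.2 calls proteins statistically significant at an unadjusted p<0.05 and leaves the test's pairing undefined; if the list rests on p alone, about 5% of unaffected proteins are declared by chance

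*Combined protocol and SAP*

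**What the plan says.** Section 9 (Analysis of the Study) makes plasma total cholesterol the primary outcome and adds: "Secondary outcome measurements will be changes in proteomics", among others. It also says "Each subject will serve as their own control". Section 6 (Laboratory Methods) lists research tests that may be run, beginning "PHA stimulation whole blood, LC-MS-based proteomics". It gives no number of proteins.

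Section 9.2 first describes a Student's t-test "to compare the difference in mean changes between the baseline and the end of each arm period while accounting for period and group effects". A separate sentence covers proteomics: a paired "t-test to identify proteins with statistically significant" changes in normalized spectral counts, at p<0.05. That sentence goes on to say that a change of at least "1.3~1.5-fold will be considered as a physiologically meaningful change to continue the study". The next one reads: "The study will be stopped if the changes are not statistically significant or the changes is smaller than 1.3-fold". Section 9.1 also ties the size of the proteomic change to the decision to continue, at an interim look after 10 completers out of a planned 20 evaluable subjects.

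The document mentions no false discovery rate, family-wise control or other adjustment for the number of proteins. It does not say which two measurements form the pair.

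**The concern.** An LC-MS proteomics run yields many proteins, and each is tested at 0.05. Calling every protein below that line statistically significant mixes real changes with chance hits, and nothing in the plan tells the reader how many of each to expect. The pilot exists to inform a possible larger trial, so a list of this kind could steer that trial towards proteins that did not change.

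The missing pair is a second gap. If the pair were before and after one oil, the test would count time effects and the omega-3 that both oils supply. Table 4 in Section 3.1 gives this row in g/day, control oil then saury oil: "Total omega-3 | 2.7 | 2.8". A protein moved equally by both oils would then be credited to LCMUFA. A multiplicity correction does not cure that.

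**Working it through.** **Inputs from the document.** Threshold 0.05 per protein; 20 evaluable subjects, with an interim at 10; fold cut 1.3 to 1.5, with 1.3 in the stop rule; omega-3 of 2.7 and 2.8 g/day. The plan gives no effect size, SD or error rate for proteomics, so it has no figure to reproduce.

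**Assumptions (not in the document).** Proteins tested m = 200 (also 50 and 400); SD of the per-subject log-ratio 0.2 to 0.5; five or twenty truly changed proteins, each 1.5-fold; two-sided tests; independent proteins unless stated.

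**1. Chance rate.** Expected false declarations = 0.05 × number of unaffected proteins. With no true effect this is 2.5, 10 and 20 for m = 50, 200 and 400. A simulated null paired t-test rejects 4.9% of the time at n = 10 and 5.1% at n = 20. The 5% needs no protein count and does not depend on correlation.

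**2. False share of a list taken on p alone, n = 20, m = 200.**
- Five true: 0.05 × 195 = 9.75 false. At SD 0.4 about 4.95 true are found, so 9.75/(9.75 + 4.95) = 66%. The simulated mean share is 65%.
- Twenty true: 0.05 × 180 = 9 false against nearly 20 true, or about 31%. Simulated 30 to 32%.
- Five true, other counts: about 29% at m = 50 and 80% at m = 400.
- Five true of 200 with correlation 0.5 between proteins: still 9.5 to 10.0 false on average, but the mean share falls to 45 to 48%.

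**3. Adding the 1.3-fold cut.** ln 1.3 = 0.262. The standard error is SD/√20 = 0.067, 0.089 and 0.112 at SD 0.3, 0.4 and 0.5, so the cut lies 3.91, 2.93 and 2.35 standard errors from zero. The two-sided normal tails times 195 give about 0.02, 0.65 and 3.7 false proteins. Requiring p<0.05 as well brings the last to 3.4.

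Simulation, five true of 200, n = 20 (true found / false / mean false share):

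| SD | p<0.05 only | p<0.05 and 1.3-fold | BH q<0.05 |
|---|---|---|---|
| 0.3 | 5.00 / 9.68 / 64% | 4.92 / 0.02 / 0.3% | 4.88 / 0.30 / 5% |
| 0.4 | 4.95 / 9.74 / 65% | 4.72 / 0.65 / 10% | 3.60 / 0.25 / 5% |
| 0.5 | 4.65 / 9.69 / 66% | 4.45 / 3.41 / 41% | 1.85 / 0.16 / 5% |

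At SD 0.2 the joint rule leaves essentially no false proteins and keeps 4.99 of the 5 true ones.

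**4. Pairing.** Suppose both oils change a protein 1.2-fold and LCMUFA adds nothing. If the between-treatment contrast has SD 0.3 or 0.4, and the two periods' changes are independent, one period's change has SD 0.3/√2 = 0.212 or 0.4/√2 = 0.283. With ln 1.2 = 0.182 and n = 20, the effect is 3.84 or 2.88 standard errors. A before/after test declares the protein 95% or 78% of the time (5% or 10% with the 1.3-fold cut as well). A between-treatment test declares it 5% of the time.

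**5. Interim.** If one protein with p<0.05 and 1.3-fold were enough to continue, and no protein truly changed, the chance of continuing at n = 10 with 50 to 400 proteins is about 1% or less at SD 0.2, 23 to 88% at SD 0.3 and 72 to 100% at SD 0.4. The plan does not say how many proteins must qualify.

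**The case against.** The strongest reply is that Section 9.2 joins p<0.05 and the fold cut in one sentence and uses both in the stop rule, so the intended criterion may be joint. On that reading false hits nearly vanish at SD 0.2 to 0.3. With twenty true proteins and SD 0.4 the false share is only about 3%. That stands as a possible reading, but the text ties the fold cut to continuing the study and does not make it a filter on reported proteins. Even the joint rule protects the list only if the assay is precise, and no SD is given.

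It is also fair that a pilot screen may favour sensitivity. At SD 0.4, Benjamini-Hochberg finds 3.6 of 5 true proteins, against 4.7 for the joint rule. This argues against dropping nominal hits. It does not argue for calling them statistically significant.

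Finally, 1.3 was never stated for a between-treatment contrast, so imposing it there would create a new threshold. That objection is accepted in the fix.

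A reader might go further and infer that most reported proteins are false, that a decision to continue was a chance result, or that the plan prescribes a before/after test. The document supports none of these. The false share depends on the number of true changes, the number of proteins and the SD, all unstated. The interim rule does not say how many proteins must qualify. The statement in Section 9 that subjects are their own controls makes the between-treatment pair the more natural reading.

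**Conclusion.** The point holds in a limited form. As worded, Section 9.2 attaches the label statistically significant to single-protein tests at 0.05 with no multiplicity control. It also leaves the pair and the period adjustment undefined for proteomics. The 5% chance rate among unaffected proteins is firm for a list taken on p alone. Every false share, and every count beyond that rate, rests on the assumed protein number, SD, number and size of true changes, and correlation.

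Severity is minor to moderate. Section 10.6 says the study is closed to accrual and in data analysis only, so the reporting can be corrected without new data.

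**What to change.** In Section 9.2, for the reported proteomics analysis:

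- (a) Test each protein on LCMUFA change minus control change, with the same period adjustment as the other outcomes. State the scale used and how zero counts are handled.
- (b) Report the number of proteins tested, and give a Benjamini-Hochberg q-value beside each p-value and fold change.
- (c) Use the term statistically significant only for q<0.05. List proteins with p<0.05 but q≥0.05 as exploratory.
- (d) Show the fold change for every listed protein and flag those at or above 1.3, without making 1.3 a requirement on this contrast. Section 3.1 allows results to be unblinded after both arms, so a cut chosen now could be driven by the data.

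For the interim, report only how the rule was applied: proteins tested, proteins that passed, pairing and fold cut. Do not cite a decision to continue as evidence of an LCMUFA effect.

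The cost is plan wording and a few lines of code. Fewer proteins will carry the label: with five true proteins of 200 at SD 0.4, about 3.6 instead of 5.0 on p alone. None is removed from the report, so no lead is lost for planning the next trial.

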10.1 Rationale for Subject Selection

Subjects of all genders will be considered for inclusion in this study. There will be no racial, ethnic, or gender discrimination. Cognitively impaired and institutionalized persons will not participate in this study. Criteria for exclusion or withdrawal from the study are based on the presence of other disease processes that may interfere with the interpretation of our results or situations that may be harmful to the health of subjects.

10.2 Rationale for the Exclusion of Children

Participant older than 18 will be considered for inclusion in this study. There is not sufficient supporting data to establish normal levels, an upper limit or safe intake of fish oil/omega-3 fatty acids in children.

10.3 Rationale for the Exclusion of Pregnant Women

Subjects must not be pregnant or actively seeking pregnancy in order to participate in this study. Pregnancy may introduce unpredictable effects on lipoprotein metabolism and influence the results of the study. The specific effects of pregnancy in this context may be the subject of a separate study. Some form of contraception must be used by subjects while enrolled. Contraception use will be determined by a questionnaire given to the subjects at time of enrollment.

